All primary analyses will be performed using intent-to-treat principles. All variables will first be assessed for evidence of outlier values or skewed distributions. Baseline characteristics and potential confounders will be summarized for participants randomized to Group 1 versus Group 2 using standard methods such as means/standard deviations and medians/inter-quartile ranges for continuous variables and frequencies with percentages for categorical variables. Differences between the groups at baseline will be statistically tested using t-tests for continuous variables or non-parametric alternatives as indicated and Chi-square tests for categorical variables. Any differences detected will be adjusted for in multivariable models. Our primary analytic approach will be mixed effects linear regression which will enable efficient estimation of treatment effects, inclusion of all study participants in intent-to-treat analyses, and the same analytic approach to be used for all three Aims. Analyses will focus on differences in outcomes when participating in PLIE vs. UC. Fixed effects terms will be included for treatment (PLIE vs. UC), sequence (Group 1 vs. Group 2), time (baseline, 4 months, 8 months) and the interaction between treatment*time. Subjects will be modeled as random effects. Models also will adjust for any baseline differences in demographic factors or confounders that may occur due to chance. Covariates will be included to adjust for any co-interventions that occur (e.g., medication changes), and sensitivity analyses will be performed excluding participants who experience co-interventions. Standard diagnostic tests will be performed to examine model assumptions and distributions of residual values and to assess for potential leverage and influence points. To minimize the risk of Type I error due to multiple comparisons with co-primary outcomes, we will adjust p-values using bootstrapping (SAS Proc Multtest).

12.4 If this study has undergone scientific or scholarly review, please indicate which entity performed the review:

- Cancer Center Protocol Review Committee (PRC) (Full approval is required prior to final CHR approval for cancer-related protocols.)
- CTSI Clinical Research Center (CRC) advisory committee
- Departmental scientific review
- Other:

Specify **Other**:

Department of Veterans Affairs; SFVA R&D Committee

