Adherence, Adverse Events and Co-Interventions. Adherence will be monitored using class attendance logs. Adverse events will be assessed by calling caregivers on a monthly basis using a standardized questionnaire. Caregivers will be asked to report changes to the participant's health status since the last contact, including any emergency room visits, hospitalizations, or injuries. For any symptoms or events reported, caregivers will be asked if they occurred during or shortly after participating in PLIE or usual activities. Events that are serious and unexpected will be reported to an independent Data Monitoring Committee (DMC) and the IRB within 5 working days. The DMC also will review the adverse event log on a biennial basis. Based on consultations with the SFVA Research Office, adverse events that are possibly, probably or definitely study-related that occur in SFVA patients will be entered as notes into the medical record. Co-interventions also will be assessed during monthly caregiver check-ins using a standardized questionnaire that asks about any changes since last contact that might affect study outcomes including changes in medications, caregivers, medical conditions, usual activities or other factors.

Video-recording. Some of the exercise classes or assessments will be video-recorded for quality control, research or educational purposes. Everyone must consent to the video-recording for quality control and training purposes. The participants will have the option to allow for (1) private viewing only – viewing limited to the research team, auditors, and monitoring committee, or (2) private and public viewing – viewing available to the public as videos will be included in the training manual, shown at research or educational meetings, and/or posted on the study website.

Participant options for video recording will be tracked together with the main consent; i.e., that tracking will be included in the current study database. More specifically, the database includes a Consent section, under which the main consent, video recording options, and future contact consent options will be entered. This will ensure that the research team are kept informed of participant choices for video recording. Participants may be contacted after study ends regarding information about the optional participation in ongoing community classes, Participants will be sent birthday cards, and--in case of death or hospitalization--sympathy cards.

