22.0 Informed Consent

22.1 * Methods (check all that apply):

- Signed consent will be obtained from subjects and/or parents (if subjects are minors)
- Verbal consent will be obtained from subjects using an information sheet or script
- Electronic consent will be obtained from subjects via the web or email
- Implied consent will be obtained via mail, the web or email
- Signed consent will be obtained from surrogates
- Emergency waiver of consent is being requested for subjects unable to provide consent
- Informed consent will not be obtained

22.2 * Process for obtaining informed consent:

The participant and LAR will participate together in the consent process. Research staff will review the key points of the consent documents and will ask if the participant or LAR have any questions. Research staff will then ask questions of the participant to assess their capacity to consent. The assessment form is included for review. If the participant demonstrates capacity to consent, they will sign the consent form; if not, they will be informed that the LAR is being asked to sign on their behalf, and the participant will be asked to assent to study procedures. The LAR may participate as the study caregiver or may designate another person (e.g., another family member, paid caregiver) to participate on their behalf. Because caregivers also will be actively participating in the study (by providing information about the participant behaviors, stress, etc.), they will sign a separate consent form. If the LAR is unable to participate in the consent visit in person (e.g., lives remotely), the consent forms may be mailed to them, reviewed with the research team over the phone, signed and mailed back; however, the participant must still provide assent. The study caregiver may also choose to have the consent form mailed to them, reviewed by phone, signed and mailed back. Finally, research staff will sign both forms and will indicate that an assent discussion was completed if appropriate.

22.3 * How investigators will make sure subjects understand the information provided to them:

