6. Capacity to consent is determined based on four criteria: whether the participant a) made a choice to participate; b) showed understanding of the research study procedures; c) demonstrated the ability to reason regarding whether or not to participate; and d) showed an appreciation for the risks/benefits of participating.
7. If the participant demonstrates capacity to consent based on these four criteria, they are asked to sign the consent form for themselves.
8. If the participant does not demonstrate capacity to consent for themselves, they are asked to assent to participation in the study, and the surrogate decision maker is asked to sign the consent form on the participant's behalf. The surrogate decision maker is also asked to complete the Self-Certification of Surrogate Decision Makers form and, if eligible, to sign the HIPAA form on the participant's behalf.
9. If the participant appears to dissent, they are not eligible to participate in the study, even if the surrogate signs the consent form. Signs of dissent may include verbal statements as well as non-verbal cues such as shaking their head no or appearing to be agitated or distressed.
10. The process of assessment of capacity to consent is documented on the Capacity Assessment Form.

23.5 Plans for obtaining consent from subjects who regain ability to consent after a surrogate has given initial consent:

Dementia is a progressive, neurodegenerative disease. Once capacity to consent has been lost, it is highly unlikely that it will be regained. Therefore, we do not plan to reassess capacity to consent. However, we will continuously assess assent to study participation. Participants will never be forced to participate in the exercise classes or other study procedures. They may decline to attend the exercise classes on a given day or may leave the room if they do not want to continue. In addition, assessment of outcomes will be discontinued if there is evidence of distress or lack of assent.

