We will use the following hierarchy if the primary participant, legally authorized representative or caregiver differ regarding their desire to continue participation. 1) If the primary participant wishes to stop participating in the study (i.e., no longer consents/assents), the dyad will be withdrawn, regardless of the preferences of the caregiver or legally authorized representative. 2) If the primary participant does not demonstrate capacity to consent and the legally authorized representative wants the primary participant to stop participating in the study (i.e., withdraws consent on their behalf), the dyad will be withdrawn, regardless of the preferences of the primary participant or the caregiver. 3) If the caregiver wishes to stop participating in the study but the primary participant wishes to continue and, if the primary participant does not demonstrate capacity to consent, the legally authorized representative agrees (e.g., paid caregiver no longer wishes to be involved), then the primary participant will be allowed to continue without the caregiver's involvement.

23.6 Requirements for any study involving surrogates for obtaining informed consent. Check to acknowledge:

- Research takes place in California. All surrogates will complete the "Self-Certification of Surrogate Decision Makers for Participation in Research" form.
- Conscious subjects will be notified of the decision to contact a surrogate. If subjects object to study participation, they will be excluded even if their surrogate has given consent.
- Surrogates will not receive any financial compensation for providing consent.
- If a higher-ranking surrogate is identified at any time, the investigators will defer to the higher-ranking surrogate's decision regarding the subject's participation in the research.

For research taking place outside of California, explain how investigators will confirm that surrogates are legally authorized representatives:

not applicable.

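### The dyad withdrawal rules end willing caregivers' own Aim 2 reports, and let a participant continue without the only stated source of adverse-event and co-intervention reports

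*Combined protocol and SAP*

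**What the plan says.** Section 23.5 ranks whose wish prevails when the parties disagree about continuing.

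- Rule 1: if the participant no longer consents or assents to the study, "the dyad will be withdrawn, regardless of the preferences of the caregiver or legally authorized representative".
- Rule 2: if the LAR withdraws a participant who lacks capacity, "the dyad will be withdrawn, regardless of the preferences of the primary participant or the caregiver".
- Rule 3: if the caregiver stops but the participant wants to go on (with the LAR's agreement where capacity is lacking), "then the primary participant will be allowed to continue without the caregiver's involvement".

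The same section keeps missed classes apart from withdrawal: "They may decline to attend the exercise classes on a given day".

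Caregivers are subjects in their own right. Section 22.2 says "they will sign a separate consent form", sections 14.6 and 14.7 give them their own eligibility criteria, and Hypothesis 2 and Aim 2 (sections 12.1 and 12.2) rest on their CBI and PAC scores. Section 16.1 adds the GDS for the caregiver's own depressive symptoms.

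Section 16.1 also sets the reporting routes. "Adverse events will be assessed by calling caregivers on a monthly basis using a standardized questionnaire". Co-interventions come from the same check-ins, and the schedule of evaluations marks both items only in the monthly check-in column. Usual-care activity has two sources, the sites' activity timetables and the caregiver. PLIÉ attendance comes from class logs.

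Section 12.3 relies on a mixed model said to allow "inclusion of all study participants in intent-to-treat analyses". It does not say how withdrawn dyads or missing caregiver outcomes will be handled.

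**The concern.** Respecting a participant's dissent requires that the participant's procedures stop. It does not by itself require that a willing caregiver's own questionnaires stop, and the plan gives no reason for ending both. A caregiver removed before month 4 leaves only a baseline score, which says almost nothing about change. Because only Group 1 is offered PLIÉ in months 0 to 4, the loss could differ between groups in the very comparison that Aim 2 needs.

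Rule 3 leaves the opposite gap. The participant stays in an exercise programme while the person whose monthly call supplies adverse events and co-interventions has left, and no replacement is named. An emergency visit, hospital stay or injury away from class then has no stated way into the log that the Data Monitoring Committee (DMC) reviews.

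**Working it through.** **1. Which caregiver reports need to stop under rules 1 and 2?** The caregiver battery in section 16.1 has two kinds of measure.

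| Subject of the report | Measures | Does participant dissent require it to stop? |
|---|---|---|
| The participant (by proxy) | DAD, NPI, proxy QOL-AD, incontinence, falls efficacy | Reasonably yes |
| The caregiver | CBI, PAC, GDS | No reason given in the plan |

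The avoidable loss is the second row, which contains both Aim 2 outcomes.

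**2. The plan's own figure for caregiver data loss.** Section 14.4 gives for CBI: effect size 0.49, 29 per group for 80% power, power 0.97 at 60 per group and 0.92 with 20% attrition. Inputs are correlation 0.75, alpha 0.03, one pre and two post measures. Sidedness is not stated; two-sided reproduces all four sample sizes in the table (12, 59, 10, 29).

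- Variance factor for change: (1 + 0.75)/2 + 1 − 2 × 0.75 = 0.375.
- n per group = 2 × 0.375 × (2.170 + 0.842)² / 0.49² = 28.3, so 29. This matches.
- Power at 60: 0.49/√(0.75/60) = 4.383; 4.383 − 2.170 = 2.213; power 0.987 (stated 0.97, within 2 points).
- Power at 48 (60 less 20%): 0.49/√(0.75/48) = 3.920; 3.920 − 2.170 = 1.750; power 0.960 (stated 0.92). This cell is not reproduced. The stated value is 4 points lower, so it errs on the cautious side.

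**3. Power at stake.** Suppose all 20% attrition (12 per group) is dyad withdrawal, and a share q of those caregivers would keep giving CBI. Then n = 48 + 12q.

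| q (assumed) | n per group | CBI power |
|---|---|---|
| 0 | 48 | 0.960 |
| 0.25 | 51 | 0.969 |
| 0.50 | 54 | 0.977 |
| 0.75 | 57 | 0.982 |
| 1 | 60 | 0.987 |

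The largest gain is 0.987 − 0.960 = 0.027, under 3 points. If there is a harm, it is bias.

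**4. Possible bias.** Let w1 and w2 be the shares of caregivers lost in each group, and δ the difference in CBI change between those lost and those kept (taken equal in both groups). A completer difference is off by (w1 − w2) × δ. The documents give none of these inputs. For an assumed excess loss in one group:

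| Excess loss | δ = 0.25 SD | δ = 0.5 SD | δ = 1.0 SD |
|---|---|---|---|
| 5% | 0.0125 | 0.025 | 0.05 |
| 10% | 0.025 | 0.05 | 0.10 |
| 20% | 0.05 | 0.10 | 0.20 |

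At the pilot SD of 14.2 (section 13.2), 0.0125 to 0.20 SD is 0.2 to 2.8 CBI points. Relative to 0.49 it is 3% to 41%. The sign depends on which group loses more, and on whether those lost are doing worse.

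**5. Rule 3 against section 16.1.**

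| Information | Stated source | Left if the caregiver stops |
|---|---|---|
| Adverse events | Monthly caregiver call | None stated |
| Co-interventions | Monthly caregiver check-in | None stated |
| Usual-care activity | Site timetables and caregiver | Site timetables; nothing for community participants at home |
| PLIÉ attendance | Class logs | Class logs |

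This part needs no assumption.

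**The case against.** Rules 1 and 2 are a defensible consent choice. The dyad is the enrolled unit, and the rule puts first the dissent of people who may lack capacity. Continuing the caregiver's self-reports is an alternative, not the correction of an error. CBI is a secondary outcome, and all of the assumed bias range lies below the 0.25 SD that section 13.2 treats as clinically meaningful. On rule 3, research-employed instructors attend every class with at most five participants each, and stop or modify exercises on signs of pain. The Data and Safety Monitoring Plan (18.1) requires prompt reporting of serious or unexpected events whatever their source. Sections 16.1 and 22.2 let the LAR designate someone else as caregiver.

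Much of this stands, and it limits the point. It does not close it. Events away from class remain without a stated route, and the provision for designating another caregiver concerns enrolment and consent, not a caregiver who leaves later.

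A reader might also infer more than the documents support:

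- *That the loss is known to be selective, or to favour PLIÉ.* No withdrawal rates by group are given. The pilot had one withdrawal among 12, in the PLIÉ group, with no reason stated. Waitlisted dyads could leave too.
- *That disliking the classes removes the caregiver.* Declining a class is not withdrawal from the study under section 23.5.
- *That intent-to-treat is broken.* The mixed model keeps data gathered before withdrawal and is valid if missingness depends only on observed data. The commitment is weakened, not breached.
- *That section 14.6 is contradicted because it calls caregivers' participation necessary.* That sentence explains why non-Veteran caregivers are enrolled. It sets no rule on continuing.
- *That the caregiver is the only source on contamination.* Site timetables are a second source, except for community participants at home.

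**Conclusion.** The point holds as a cheap improvement in two parts. First, rules 1 and 2, followed as written, give up caregiver self-reports that could be kept. Unequal loss between groups is possible but undocumented, and the figures in the working are illustrations that rest wholly on assumed loss rates and differences in change. They describe a completer comparison; a mixed model will do better to the extent that observed scores predict who leaves. Second, and more firmly, rule 3 and the adverse-event procedure in section 16.1 do not fit together: one lets the caregiver leave, and the other depends on the caregiver. That follows from the text alone.

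**What to change.** - **Section 23.5, rules 1 and 2.** Keep the rule that all participant procedures and all proxy reports about the participant end. Add that a caregiver who still consents is invited to complete their own CBI, PAC and GDS at 4 and 8 months, analysed in the group to which the dyad was randomised.
- **Section 12.3.** State how withdrawn dyads and missing caregiver outcomes are handled.
- **Section 23.5, rule 3.** Reconcile it with section 16.1 by naming a substitute informant, the LAR or another caregiver, for the monthly adverse-event and co-intervention call.

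The cost is an amendment, consent-form wording and a few extra contacts after a participant or caregiver stops. Caregiver assessments can already be done by phone or mail (section 16.1), and 15-minute monthly calls are already planned (section 16.6). Participant dissent remains fully respected.

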23.7 VA Studies Only

Provide any additional information to explain comply with the additional VAMC requirements for use of surrogates in research:

All study procedures will conform to the guidelines in VHA Handbook 1200.05, including section 36 on surrogate consent and section 49 on research involving persons who lack decision-making capacity.

Surrogate Consent (section 36)

a) Assessment of Capacity. Detailed procedures are provided above describing our procedures for assessment of capacity to consent.

b) Investigators' Responsibilities for Surrogate Consent. Prior to engaging in the consent process, we will inform all LARs about their roles and obligations. Specifically, that their obligation is to try to determine what the potential participant would do if they were able to make their own decision; and that if they are unsure, then they should determine what is in the potential participant's best interests.

c) LARs. Consistent with VA guidelines, we will use the following order of priority to identify the most appropriate LAR: health care agent (i.e., individual named in Durable Power of Attorney for Health Care); legal guardian; next of kin in the following order: spouse, child, parent, sibling, grandparent, grandchild; or close friend.

d) Dissent or Assent. As described above, all study procedures will be explained to potential participants, and we will seek their assent to participate if they are unable to consent for themselves. Study participants who show evidence of dissent (e.g., shaking head no, appearing agitated or distressed) or who resist participating will never be forced to participate, even when the surrogate gives consent.

e. Fluctuating Capacity. As described above, dementia is a progressive, neurodegenerative disease. Once capacity to consent has been lost, it is highly unlikely that it will be regained. Therefore, we do not plan to reassess capacity to consent. However, we will continuously assess assent to study participation. Participants will never be forced to participate in the exercise classes or other study procedures. They may decline to attend the exercise classes on a given day or may leave the room if they do not want to continue. In addition, assessment of outcomes will be discontinued if there is evidence of distress or lack of assent.

Research Involving Persons Who Lack Decision-Making Capacity (section 49)

a) IRB Review and Approval: Individuals who lack decision-making capacity will not participate until the IRB has approved their participation

b) Criteria for Decision-Making Capacity: We will consult with the adult day health facility director at each site about each individual's decision-making capacity before proceeding with the informed consent process.

c) Temporary or Fluctuating Lack of Decision-Making Capacity: Please see above.

d. Criteria for Enrollment. The study entails minimal risk, and the potential for benefit is greater than the potential for risk. In addition, the disorder that has caused the participants' lack of decision-making capacity is being studied, and the study cannot be performed with only people who have decision-making capacity.

e. IRB Determination. The study includes appropriate procedures for obtaining assent and assessing dissent on an ongoing basis.

If the participant lacks capacity, the HIPAA can only be signed by the durable power of attorney, advance health directive agent, or legal guardian.

24.0 Financial Considerations

24.1 Subjects payment or compensation method (check all that apply):

Payments will be (check all that apply):

- Subjects will not be paid
- Cash
- Check
- Debit card
- Gift card
- Reimbursement for parking and other expenses
- Other:

Specify **Other**:

24.2 Describe the schedule and amounts of payments, including the total subjects can receive for completing the study. If deviating from recommendations in Subject Payment Guidelines, include specific justification below.

Participants will not be paid to participate in the study. The PI received feedback from participants that incentives are not important factors for their participation in the study. Additionally, the research team has encountered significant challenges with procuring these incentives, and we are no longer able to utilize the same mechanism for obtaining the incentives. Between these challenges and the feedback we received from the study participants, the research team is removing the incentives all together.

24.3 Costs to Subjects: Will subjects or their insurance be charged for any study procedures?

Yes No

If **yes**, describe those costs below, and compare subjects' costs to the costs associated with alternative care off-study. Finally, explain why it is appropriate to charge those costs to the subjects.

